5. STUDY DESIGN

5.1 Overview

We will evaluate the effect of a bidirectional conversational agent (“Penny”), compared to usual care, on patient adherence to oral targeted therapies using a two-arm randomized-controlled trial (Aim 1), and explore how multilevel factors impact the effectiveness and implementation of the strategy by collecting qualitative and quantitative data from clinicians and patients (Aim 2). The intervention will leverage a third-party company, Memora Health, who have developed a HIPAA-compliant, SMS text-based platform and worked previously with Penn Medicine. Consented patients with advanced lung cancer receiving oral targeted therapies within UPHS will be randomized (1:1) to Penny or usual care. Longitudinal adherence outcomes for all participants will be captured using microelectronic monitoring system (MEMS) caps, surveys, and EMR data. Following active intervention, semi-structured interview data will be collected from a subsample of 30 patients and 30 clinicians to further assess mechanisms shaping adherence, and the acceptability, effectiveness, and future implementation of Penny into routine cancer care.

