5.2 Study Setting

The study will be conducted at two hospitals affiliated with the University of Pennsylvania Health System: Perelman Center for Advanced Medicine/Hospital of University of Pennsylvania (PCAM) and Penn Presbyterian Medical Center (PPMC).

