5.4 Target Population

Aim 1. The study aims to enroll 170 adult patients (18 years or older) with advanced NSCLC who have initiated oral targeted therapies at UPHS. These include afatinib, erlotinib, dacomitinib, gefitinib and osimertinib for patients harboring sensitizing EGFR mutations; and alectinib, brigatinib,, crizotinib, and lorlatinib for patients with anaplastic lymphoma kinase (ALK) or ROS1 rearrangements. To be eligible, participants must be receiving ongoing cancer care at a participating site; have access to a mobile phone with SMS text messaging capabilities; be able to read and respond to questions in English; and must have started taking oral targeted therapies no earlier than January 1, 2020 and no later than the end of study recruitment (estimated October 2021).

Aim 2. The study aims to interview 30-45 patients and 15-30 clinicians. Patients will be eligible if they are enrolled in the intervention trial (Aim 1). Clinicians will be eligible if they actively provide care for cancer patients on targeted oral therapies at one of the study sites (including but not limited to oncologists, advanced practice providers, triage nurses, and pharmacists).

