5.5 Sample Size and Accrual

Aim 1. The study sample will be drawn from adults seeking cancer care at the University of Pennsylvania's Abramson Cancer Center (ACC). Across recruitment sites, approximately 215 patients with lung cancer had orders for one of the included oral targeted therapies from January-September 2020. For this study, we will include both patients who have new prescriptions (after study launch) and patients previously taking these medications in 2020 (and who continue to take these medications at the time of eligibility assessment). Based on preliminary studies with Penny, we conservatively estimate that $\geq 40\%$ of patients approached will be eligible and consent to participate in this study. Of the 215 patients who started taking these medications in 2020 and estimated number of new starts during the study enrollment period (estimated 25 new starts per month), we anticipate that we will reach our target sample size of 170 in approximately 9-12 months (enrolling an estimated 85 patients who are currently taking these medications and 10 patients monthly who are new medication starts across the enrollment period). Allowing for a 15% loss to follow up, 72 participants will remain in each arm ($n=144$). Our full sample will provide 80% power to detect minimum effect of 20.9% or greater between the intervention and control group (assuming previously observed 65.5% adherence rate in controls and using fisher's exact test⁷), an effect size that is clinically significant and appropriate for this pilot stage of research.

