6.2 Assignment

Participants will be randomized individually to 1 of the 2 arms using REDCap randomization module, stratified by three conditions: 1) medication status (new or prevalent starts), 2) drug class (ALK vs ROS1), and 3) study hospital (PCAM vs PPMC). Enrolled patients will learn their assignment (open label) following completion of the baseline survey.

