9. ANALYSIS PLAN

9.1 Primary Analyses

Our primary analyses will use an intent-to-treat (ITT) approach using repeated measures logistic regression to compare the overall effect of the intervention on patient adherence. We will also explore potential differences in secondary outcomes across arms. Baseline clinical and survey data will be used

to assess potential differences in treatment groups (i.e., socio-demographics and clinical risk factors) using parametric or nonparametric tests as appropriate. Data quality, normality, and other assumptions will be assessed prior to analysis. Using repeated measures logistic regression fitted using generalized estimating equations (GEE), we will compare the proportion of adherent days between Penny and usual care. Data will be treated as binary outcome (0/1) over the study period. Models will contain a predictor term for treatment arm, will be adjusted for time (discrete week), and will contain subject specific random effects and fixed effects for site. Patients will be categorized as adherent (outcome=1) across the study period if the total percentage of adherent days is $\geq 95\%$ similar to previous studies⁷; other percentages (80%, 90%, 100%) will be explored in sensitivity analyses. Persistence will be treated as repeated measure survival data and will be summarized as median survival time using Kaplan-Meier methods. We will also generate summary statistics (including mean adherence rate) to help describe the study population and inform the design of further studies.

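### The primary model adjusts for hospital but leaves out the other two randomisation strata, medication status and drug class; if these predict adherence, the test is slightly conservative and gives up some power.

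*Combined protocol and SAP*

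**What the plan says.** Section 6.2 (Assignment) randomises individuals in REDCap, "stratified by three conditions: 1) medication status (new or prevalent starts), 2) drug class (ALK vs ROS1), and 3) study hospital (PCAM vs PPMC". Section 9.1 (Primary Analyses) gives the terms of the primary model in one sentence: "Models will contain a predictor term for treatment arm, will be adjusted for time (discrete week"), and the model "will contain subject specific random effects and fixed effects for site". Site is the hospital stratum, since section 5.2 states: "The study will be conducted at two hospitals affiliated with the University of Pennsylvania Health System".

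No primary or sensitivity analysis is said to adjust for medication status or drug class. The baseline comparisons in section 9.1 only describe differences between groups, and the interaction models in section 9.2 are exploratory.

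Two further passages bear on the point. Section 5.5 expects about half the sample to be prevalent users: "enrolling an estimated 85 patients who are currently taking these medications and 10 patients monthly who are new medication starts". Section 5.4 admits patients on EGFR drugs ("afatinib, erlotinib, dacomitinib, gefitinib and osimertinib for patients harboring sensitizing EGFR mutations") as well as those with ALK or ROS1 rearrangements, so the two drug-class levels in section 6.2 do not cover everyone who can enrol.

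**The concern.** Stratified randomisation balances the arms on the stratification factors. If those factors predict the outcome, the estimated treatment effect varies less between hypothetical repeats of the trial than an analysis that ignores them assumes. The standard error is then too large for the design, the test rejects less often than 5% under the null, and power is lost. The plan accepts this logic for hospital but applies it to one factor of three, without giving a reason.

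The subject-specific effects do not replace the missing terms. They describe correlation within a person and do not remove the between-person variation that medication status and drug class would explain.

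What is at stake is modest: some power in a trial with 144 evaluable patients and a 20.9-point detectable difference. There is no threat of a false positive in favour of Penny.

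**Working it through.** **Inputs from the documents.** 170 enrolled, 1:1; 15% loss, leaving 72 per arm; 65.5% adherent in controls; 20.9-point difference, so 86.4% with Penny; adherent means at least 95% of days (sections 5.1, 5.4, 5.5, 8.3). Prevalent users 85/170 = 50% (section 5.5).

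**Assumptions, not in the documents.** Two-sided 5% test; drug class split 20/80 or 50/50; hospital not prognostic; medication status and drug class each carrying the same odds ratio (OR) for adherence, varied from 1 to 3.

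**Step 1: the plan's own figure.** Dropout: 72/(1 − 0.15) = 84.7, rounded up to 85 per arm, 170 in all. Fisher's exact power is the sum, over all pairs (x, y), of Bin(x; 72, 0.655) × Bin(y; 72, 0.864) where the two-sided p-value is at most 0.05. Full enumeration gives 0.8003, and the smallest difference with 80% power is 20.9 points. The stated figure reproduces and does not depend on the strata.

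**Step 2: outcome model.** With arm A, medication status M and drug class D coded 0/1:

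logit P(adherent) = α + τA + β(M + D), β = ln(OR)

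α and τ are solved so that the rates averaged over the strata are 65.5% and 86.4%. Example, OR 3 with 50/50 splits: α = −0.369 and τ = 1.329. Control rates in the four M × D cells are 40.9, 67.5, 67.5 and 86.2% (mean 65.5%); Penny rates are 72.3, 88.7, 88.7 and 95.9% (mean 86.4%).

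**Step 3: comparison.** 100,000 trials per scenario, arms balanced within the 8 cells of medication status × drug class × hospital. Patient-level logistic regression on arm + hospital was compared with arm + hospital + medication status + drug class, by Wald test. Simulation error is about √(0.85 × 0.15/100,000) = 0.11 points on power and √(0.05 × 0.95/100,000) = 0.07 points on type I error. Ranges cover the two drug-class splits.

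| OR per factor | Type I error, hospital only | Power, hospital only | Power, all strata | Gain at 86.4% (points) | Gain at 80.5% (points) |
|---|---|---|---|---|---|
| 1 | 4.9% | 84.6% | 84.9% | 0.3 | 0.4 |
| 1.5 | 4.7–4.8% | 84.4–84.8% | 85.0–85.5% | 0.6–0.7 | 0.9–1.0 |
| 2 | 4.3–4.4% | 84.9–85.0% | 86.0–86.3% | 1.1–1.4 | 1.7–2.1 |
| 3 | 3.7–3.9% | 84.9–85.8% | 87.0–88.3% | 2.1–2.5 | 3.7–4.6 |

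The last column takes a true effect of 15 points (65.5% + 15 = 80.5%), which is smaller than planned. The adjusted model's type I error is 5.0–5.2%, so part of the gain is the return of the test to its nominal level. If only medication status matters, OR 3 gives 1.5–1.6 points at the planned effect. Robust standard errors, in a separate run of 40,000 trials, gave the same rejection rates within 0.1 point.

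**Step 4: where the gain comes from.** Adjustment does not shrink the standard error of the log-odds ratio. At OR 3 (50/50 split) it rises from 0.429 to 0.459, while the estimate moves from 1.23 to 1.38. The ratio goes from 1.23/0.429 = 2.87 to 1.38/0.459 = 3.01.

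**Step 5: less exact balance.** With 170 enrolled, blocks of 4 (assumed) and 15% random loss, hospital-only type I error was 4.8% at OR 2 and 4.1–4.3% at OR 3. Power gains were 1.0–1.2 and 2.0–2.6 points. The type I error is nearer nominal than in the table; the gains are about the same.

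**The case against.** The best case against the point has four parts.

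- **The model simulated is not clearly the one planned.** Section 9.1 describes a weekly repeated-measures model for adherent days and also a single yes/no value per patient at the 95% cut-off. It names both GEE and subject random effects, which are different models. The figures here belong to the patient-level version. This stands: the direction should carry over, but the decimals may not.
- **The change is not wholly without cost.** The adjusted odds ratio is conditional on the strata, so the quantity reported changes (1.23 to 1.38 on the log scale in the example). Only about 35 non-adherent patients are expected (72 × 0.345 + 72 × 0.136 = 24.8 + 9.8). If one drug class were as rare as 5% (an assumption), its coefficient diverged in 17–46% of simulated trials at the planned effect, although the arm test stayed usable. This stands as a matter for the wording of the fix.
- **Drug class cannot be coded yet**, because its levels in section 6.2 do not match the population in section 5.4. This stands too. Only the medication-status term could be added as the documents read now.
- **The benefit is hypothetical.** Nothing in the documents shows that either factor predicts adherence, and at OR 1.5 or below the gain at the planned effect is under 1 point in a self-described pilot. This is true and limits the weight of the point. It does not answer it, since the simulations show essentially no loss when the factors are irrelevant.

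**Conclusion.** The concern holds as a minor one, worth considering. The primary model follows one of the three factors used to randomise, and no reason is given. If medication status and drug class do not predict adherence, almost nothing is lost. If each has an odds ratio of 2 to 3, the hospital-only test runs at roughly 3.7–4.8% rather than 5%, and about 1 to 2.6 points of power are forgone at the planned effect. More is forgone if the true effect is smaller. There is no bias or inflated type I error, and the stated 80% power is unaffected.

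The omission itself is certain from the text. Its size depends on the assumed odds ratios, the drug-class split, a two-sided 5% test and a patient-level outcome.

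**What to change.** 1. Reconcile the drug-class levels between sections 6.2 and 5.4, and record the levels that REDCap actually used.
2. In section 9.1, add medication status and drug class as fixed effects alongside site in the primary model, coded as in the randomisation.
3. In the same edit, say whether the reported odds ratio is conditional on the strata, give a rule for a sparsely filled drug-class level, and settle whether the model is GEE or has random effects.

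The cost is SAP wording and two degrees of freedom, or three if drug class turns out to have three levels. Both factors have to be recorded in order to randomise, so no new data are needed. Specifying them in advance also avoids a later choice of covariates.

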4.3 Secondary Outcome

The secondary outcome is persistence defined as the number of consecutive days on the prescribed medication regimen and conversely gaps in overall treatment.

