5.3 Study Duration

Aim 1: Study enrollment for each participant will last approximately 15-weeks including consent and post-assessment. Observation will begin no earlier than one week after therapy initiation (to allow for a brief prescription run-in period for new starts) and end either 12-weeks later or at therapy discontinuation, whichever is shorter. Post-assessment will occur within 2 weeks after each patient's active observation period. We anticipate the active trial will last approximately nine months, with anticipated enrollment beginning in November-December 2020 and ending in October 2021. Data ascertainment and analyses will continue through December 2021 or later as needed.

Aim 2: Study enrollment for each interview participant will last approximately 60-90 minutes including consent, semi-structured interview, and completion of brief written questionnaire. We anticipate that interviews will begin in December 2020 and continue through November 2021. Analyses will continue through December 2021 or later as needed.

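### Persistence is summarised by a Kaplan-Meier median with no defined event, gap length or handling of repeated spells, so the median may be unreachable in 84 days or rest on correlated spells

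*Combined protocol and SAP*

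**What the plan says.** Section 4.3 sets the outcome: "The secondary outcome is persistence defined as the number of consecutive days on the prescribed medication regimen and conversely gaps in overall treatment". Section 8.3 repeats this definition without adding a rule. The whole analysis is one sentence in Section 9.1: "Persistence will be treated as repeated measure survival data and will be summarized as median survival time using Kaplan-Meier methods". On comparing arms, the same section says only: "We will also explore potential differences in secondary outcomes across arms".

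Section 5.3 has each patient's observation "end either 12-weeks later or at therapy discontinuation, whichever is shorter".

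A method that handles correlated observations is named for adherence alone: "Using repeated measures logistic regression fitted using generalized estimating equations (GEE), we will compare the proportion of adherent days between Penny and usual care".

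For persistence, the documents do not state:
- what ends a spell, or the shortest gap that counts;
- whether one or several spells per patient enter the analysis;
- whether discontinuation is an event or a censoring time;
- how correlation within a patient is handled;
- which estimate or test compares the arms.

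Persistence is secondary in Sections 1 and 4.3, but the abstract (Section 2) lists it with adherence as primary.

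**The concern.** The sentence in Section 9.1 joins two things that do not fit without a further rule. Repeated-measures survival data means several times per patient. The ordinary Kaplan-Meier estimator and its Greenwood standard error assume one independent time per patient. Pooling spells would give a patient with eight short runs eight entries and a fully persistent patient one. It would also count correlated entries as independent information.

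The other natural reading is one time per patient. A median then exists only if the curve falls to 50% within 84 days, which is doubtful for an event such as stopping therapy.

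At stake is the only secondary outcome. It could be reported as a median not reached in both arms, or with a median and precision that reflect the pooling. Section 5.3 adds to the ambiguity: because observation stops at discontinuation, an analyst could code that date as an event or as censoring, with opposite meaning for persistence.

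**Working it through.** **Inputs.** Follow-up is at most 12 × 7 = 84 days (Section 5.3). Patients per arm (Section 5.5): 170/2 = 85, and 85 × 0.85 = 72.25, so 72. The control adherence rate is 65.5% and the detectable difference 20.9 points (Section 5.5), so 65.5 + 20.9 = 86.4% with the intervention. The adherence threshold is 95% of days (Section 8.3).

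**The plan's own figure.** No power, event count or expected median is given for persistence, so there is none to reproduce. The primary-outcome figure does reproduce: exact enumeration of a two-sided Fisher test, 72 per arm, 65.5% against 86.4%, alpha 0.05 (assumed), gives 80.03% power. The 72 and the 65.5% are therefore used below.

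**1. One event per patient: discontinuation.** With administrative censoring only, the median is reached if at least 36 of 72 patients have the event: P(X ≥ 36), X ~ Binomial(72, p). The documents give no p, so a range is shown.

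| Assumed 12-week discontinuation | P(median reached) | P(not reached) |
|---|---|---|
| 10%, 20% | <0.01% | >99.9% |
| 30% | 0.03% | >99.9% |
| 40% | 5.5% | 94.5% |
| 45% | 23% | 77% |
| 50% | 55% | 45% |
| 60% | 97% | 3% |

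If both arms are at 40%, at least one lacks a median in 1 − 0.0546² = 99.7% of trials.

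**2. One event per patient: a gap of 5 or more days.** A patient observed for 84 days meets the threshold with at most 4 non-adherent days (80/84 = 95.2%; 79/84 = 94.0%). Anyone with a 5-day gap is therefore non-adherent, and at a 65.5% control rate at most 100 − 65.5 = 34.5% of fully observed controls can have one. P(X ≥ 36) with p = 0.345 is 0.5%, an upper bound before counting discontinuations.

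**3. One event per patient: any missed day.** Missed days were set so that the stated share of patients has at most 4 in 84, using a beta-binomial with assumed intra-patient correlation rho. At rho = 0 the daily miss probability is 0.0461, so the control median is ln 0.5 / ln(1 − 0.0461) = 14.7 days.

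| rho | Control (65.5%): median run; P(reached) | At 86.4%: median run; P(reached) |
|---|---|---|
| 0.02 | 17 days; 100% | 37 days; 100% |
| 0.05 | 20 days; 100% | 77 days; 65% |
| 0.1 | 24 days; 100% | not reached; 3% |
| 0.2 | 33 days; 98% | not reached; 0% |
| 0.5 | 84 days; 55% | not reached; 0% |

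**4. Several spells per patient, pooled.** Two separate simulations, with all gap patterns assumed:
- *Precision and location*, using the control model of step 3 (about 4.5–5.5 spells per patient): for rho 0.02, 0.05, 0.1 and 0.2, the true variance of the day-14 estimate is 1.8, 2.6, 3.2 and 3.5 times the Greenwood variance. At rho = 0 it is 1.0 times. The pooled median is about 5–14 days, against 17–32 days for first spells.
- *Arm comparison*, with 72 per arm, no true difference, a mean of 1–3 gaps per 84 days, gamma frailty shape 0.5–1 and 3-day gaps: a nominal 5% log-rank test on pooled spells rejects in about 12–23% of trials, against about 2–6% using first spells only.

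**The case against.** The strongest reply is that the plan commits to none of these errors. A reader might infer that it treats spells as independent. It does not say so: it calls the data repeated, offers a descriptive summary, and names no test, interval or variance for persistence. The 12–23% therefore measures an analysis that could be run under the wording, not one that is written down. This stands.

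A reader might also infer that the median will usually be inestimable, or that every reading fails. Neither is supported. The definition, "persistence defined as the number of consecutive days on the prescribed medication regimen and conversely gaps in overall treatment", can be read as one time per patient to the first interruption. If any missed day counts, the control median is about 15–33 days and is reached in at least 98% of trials for rho up to 0.2. Under the gamma-frailty settings of step 4, P(no gap by day 84) = (1 + m/k)^−k for mean m and shape k, and the first-spell median is reached with probability above 50% in five of the six settings (11% in the sixth).

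The two problems also belong mostly to different readings. Discontinuation gives one event and no clustering, while short gaps give clustering and a median that is generally reached. Both arise together only if recurrent spells end at long gaps.

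Finally, a median that is not reached is a valid result, and the curve still carries information. This is a pilot with an exploratory comparison. That limits the impact, but it does not remove the need for a rule: the plan promises only the median, and the choices that decide whether it exists, and what it means, remain open.

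**Conclusion.** The concern holds as a specification fault. The plan names a summary that does not fit repeated data without a further rule, and it leaves undefined the event, gap length, censoring, unit of analysis and arm comparison.

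The size depends on the reading:
- **Pooled spells:** variance understated about 1.8- to 3.5-fold, the median pulled down, and type I error of about 12–23% if a log-rank test is used.
- **Discontinuation at 40% or less by week 12:** the median is not reached in an arm with probability of at least 94.5%.
- **A gap of 5 or more days:** at most a 0.5% chance of reaching the median in controls.
- **Any missed day:** the control median is usually reached, but at 86.4% adherence it is not if rho is 0.1 or more.

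These figures rest on assumptions outside the documents: the discontinuation rates, rho, the gap and frailty settings, administrative censoring only, and one definition of a missed day for adherence and persistence. The documents do not support the stronger statements that independence is planned or that the median will usually be missing. The change should be made, but the primary analysis does not depend on it.

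**What to change.** In Section 9.1, replace the persistence sentence with a definition and an analysis that work under any of these readings:

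1. One event per patient: time from the study start date to the first gap of a stated length or to discontinuation, whichever comes first. Count discontinuation as an event and censor at day 84. Fix the gap length in writing before unblinding.
2. Report by arm the Kaplan-Meier curve, the 12-week persistence proportion and the 84-day restricted mean persistent time, each of the last two with a 95% confidence interval for the difference. Give the median only if it is reached.
3. If gaps are analysed as repeated events, use a recurrent-event model with patient-clustered robust standard errors.
4. Stratify any test by the randomisation factors only after the drug-class stratum in Section 6.2 (ALK against ROS1) is reconciled with the EGFR drugs eligible in Section 5.4.

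The abstract should also agree with Sections 1 and 4.3 on whether persistence is primary or secondary.

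The cost is plan wording and slightly more analysis work. The MEMS data are the same, and sample size and patient burden do not change.
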